11.2.2 Adverse Events of Special Interest

The Adverse Events of Special Interests (AESI) categories will be summarized and presented for each treatment group using SMQ/CMQ/LMQ/Preferred Term.

| AESI | Type of MedDRA Query | Broad or Narrow Search | SMQ/CMQ/LMQ Search Criteria |
|--|----------------------|------------------------|---|
| Serious Infections | CMQ | | "Infection" – Subset for SAEs |
| Opportunistic Infection | CMQ | | "Opportunistic infection" |
| Herpes zoster | CMQ | | "Herpes zoster" |
| Tuberculosis | CMQ | | "Tuberculosis" |
| Malignancy | SMQ | Narrow | "Malignancies," |
| Non-Melanoma Skin Cancer (NMSC) | SMQ | Broad | Skin Malignant tumours (Broad SMQ) removing Melanoma CMQ |
| Malignancy other than NMSC | SMQ | Narrow | Malignancy and removing NMSC output |
| Lymphoma | SMQ | | "Malignant Lymphomas" |
| Hepatic Disorder | SMQ | Narrow | "Drug Related Hepatic disorders" |
| Intestinal Perforations | LMQ | | Terms for/related to any part of GI Tract, GI Ulcers, obstruction, hemorrhage |
| Anemia | CMQ | | "Non-Hemolytic and Non-Aplastic anemias" |
| Adjudicated Cardiovascular Events | Output from CAC | | |
| Neutropenia | CMQ | | "Hematological toxicity – Neutropenia" |
| Lymphopenia | CMQ | | "Hematological Toxicity – Lymphopenia (Veliparib Product Specific)" |
| Renal dysfunction | SMQ | Narrow | "Acute renal failure" |
| Rhabdomyolysis/myopathy | SMQ | Narrow | "Rhabdomyolysis/Myopathy" |
| Creatine phosphokinase (CPK) Elevation | Preferred Term | | "blood creatine phosphokinase increased" |

Additional AEs may be considered for tabulation/summary based on recommendations from Clinical and Safety as deemed appropriate.

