4.2 Design Diagram

[figure not shown]
This is a Phase 2, multicenter, randomized, double-blind, placebo-controlled study designed to evaluate the efficacy, safety, and pharmacokinetics of ABT-494 as induction

therapy in subjects with moderately to severely active Crohn's disease and evidence of mucosal inflammation defined by a SES-CD ≥ 6 (or ≥ 4 for subjects with disease limited to the ileum) and average daily soft/liquid stool frequency ≥ 2.5 or average daily abdominal pain score of ≥ 2.0 ; and CDAI ≥ 220 and ≤ 450 , with a history of inadequate response or intolerance to immunomodulators and/or anti-TNF therapy. The study will allow enrollment of up to 30% of subjects who were primary non responders to anti-TNF treatment.

The study is designed to enroll approximately 210 subjects to meet scientific and regulatory objectives without enrolling an undue number of subjects in alignment with ethical considerations. Therefore, if the target numbers of subjects have been enrolled, there is a possibility that additional subjects in screening will not be enrolled.

The study duration could be up to 60 weeks, including a Screening Period of up to 35 days, a 16-week double-blind induction period, a 36-week double-blind extension phase, and a 30-day follow-up period. Subjects who met eligibility criteria were randomized in a 1:1:1:1:1:1 ratio to one of the double-blinded induction treatment arms.

[figure not shown]
The schematics of the overall study design are shown in [Figure 1](#) and [Figure 2](#).

Figure 1. Study Design Schematic

*The 6 mg BID dose arm was added to replace the 24 mg QD dose arm in Protocol Amendment 2

**Subjects who were re-randomized at Week 16 to 24 mg QD prior to Protocol Amendment 2 will continue to receive the double-blind 24 mg QD dose until Week 52/PD.

Figure 2. Study Design Schematic for Open-Label Extension Option for Patients Who Do Not Adequately Respond During the Extension Phase

Screening Period

Within 35 days prior to the Baseline Visit, subjects received a full explanation of the study design and study procedures, provided a written informed consent, and underwent the screening procedures as outlined in [Table 1](#).

An e-diary was dispensed and training were provided to the subject at the Screening Visit.

Laboratory tests performed during the Screening period can be repeated in case the abnormalities are considered to be transient by the investigator.

16-Week Induction Period

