The central reader endoscopic score will be used for calculating the Endoscopic response for the evaluation of the efficacy endpoints. However, for stratification at the time of re-randomization, the endoscopic score at BL from central reader and the endoscopic score at Week 12 or Week 16 from site local reader will be used in order to determine response status.

Clinical response is defined as average daily liquid/soft stool frequency reduction of at least 30% from Baseline and average daily abdominal pain score not worse than Baseline OR average daily abdominal pain score reduction at least 30% from baseline and average daily stool frequency not worse than Baseline.

During this period of the study, subjects will visit the study site at Weeks 20, 28, 36, 44, and 52/Early Termination. A \pm 3-day window is permitted around scheduled study visits. The last dose of study drug is taken the evening prior to the Week 52 visit.

Subjects will be expected to remain on double-blinded therapy throughout the entire 36-week extension phase. However, subjects who are considered by the investigator to have not achieved meaningful symptomatic relief and meet the criteria for inadequate response at or after Week 20 will be eligible to receive the open-label therapy with ABT-494 12 mg BID, [Figure 2](#). Subjects who were re-randomized at Week 16 prior to Protocol Amendment 2 and are taking open-label ABT-494 24 mg QD will be transitioned to ABT-494 12 mg BID.

Subjects who still continue to meet criteria for inadequate response following a 4-week course of open-label ABT-494 12 mg BID will be eligible to dose escalate to open-label ABT-494 24 mg BID.

Subjects with persistent inadequate response while on ABT-494 12 mg BID or 24 mg BID may be withdrawn from the study at the investigator's discretion.

Criteria for Inadequate response are as follows:

- Average daily liquid/soft Stool Frequency > 2.2 OR average daily Abdominal Pain score > 1.8 AND
- An increase level of hs-CRP of at least 1 mg/L from Baseline or a hs-CRP ≥ 5 mg/L, either at the previous visit or at the current visit.

Note: hs-CRP will be performed by Central Lab. However, for the purpose of evaluating Inadequate Response criteria, hs-CRP can also be done at local lab.

Assessment of inadequate response should include consideration by the Investigator to rule out symptoms caused by reasons other than Crohn's disease related inflammation.

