The number and percent of subjects using Crohn's disease specific medications (including corticosteroids, aminosalicylates, immunosuppressants [defined as azathioprine, 6-mercaptopurine, or methotrexate], antibiotics) within past 90 days prior to the Baseline, and at the Baseline will be tabulated. In addition, the number and percent of subjects using Crohn's disease specific immunosuppressants, and biologic therapies at any time prior to Baseline will be tabulated.

8.0**Patient Disposition**

Subject disposition will be presented for subjects in the ITT and safety analysis sets using the following information by treatment group:

- Number and percent of subjects in various analysis sets by treatment group and by investigator and/or site number
- Number and percent of subjects completing extension phase and discontinuing on or before Week 52 visit.
- Subject disposition including the number and percent of subjects who prematurely discontinued the study) by primary reason and by any reason

Summary of protocol deviations will be provided.

9.0**Study Drug Exposure and Compliance**

Study drug exposure and compliance will be summarized using the mean, standard deviation, minimum, median, and maximum. Exposure to study drug will be summarized by separately for double-blind extension phase and open-label extension phase.

Compliance is defined as the number of capsules taken (i.e., the difference between the number of capsules dispensed and the number of capsules returned) divided by the number of capsules a subject is supposed to take each day times the length of time that the subject was in the Treatment Phase of the study (i.e., Final/Discontinuation Visit date during Treatment Phase – Day 1 [Baseline] Visit date + 1). Subjects with missing data for the number of capsules returned will be excluded from the summary.

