11.2 Analysis of Adverse Events**11.2.1 Treatment-Emergent Adverse Events**

Treatment-emergent AE for double-blind Extension Phase is defined as any adverse event with an onset date on or after the first dose of double-blind maintenance dose and prior to the open-label dose or up to 30 days after the last dose of double-blind maintenance dose if subject discontinued prematurely in double-blind maintenance phase.

For subjects who entered open-label due to inadequate response, treatment-emergent AEs for open-label Extension Phase will also be summarized by open-label dose. Treatment-emergent AE for open-label Extension Phase is defined as any adverse event with an onset date on or after the first dose of open-label dose and up to 30 days after the last dose of open-label dose.

An overview of treatment-emergent AEs, including AEs of special interest such as adverse events leading to death and adverse events leading to early termination, AEs by

Medical Dictionary for Drug Regulatory Activities (MedDRA version 20.0 or later) preferred term and system organ class, AEs by maximum relationship to study drug, and AEs by maximum severity will be summarized by number and percentage.

Changes in laboratory data will be summarized.

In addition, shift tables and listings will be provided for abnormal values, whereby the normal range of the analyzing laboratory will be used. Vital signs will be analyzed similarly.

The number and percent of subjects experiencing treatment-emergent adverse events will be summarized for the following adverse event categories.

- Any treatment-emergent adverse event.
- Any treatment-emergent adverse event that was rated as possibly related to study drug by the investigator (Reasonable Possibility).
- Any treatment-emergent severe adverse event.
- Any treatment-emergent serious adverse event.
- Any treatment-emergent adverse event leading to discontinuation of study drug.
- Any treatment-emergent adverse event leading to death.
- Any treatment-emergent adverse event of special interest.

Treatment-emergent adverse events will be summarized as follows:

- Grouped by System Organ Class and Preferred Term.
- Grouped by System Organ Class, Preferred Term and Severity.
- Grouped by System Organ Class, Preferred Term and Relationship to Study Drug.
- Grouped by System Organ Class and Preferred Term with subject numbers.

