In treatment-emergent AE tables, a subject who reports more than one treatment-emergent AE in different system organ classes will be counted only once in the overall total. A subject who reports two or more different preferred terms which are in the same SOC will be counted only once in the SOC total. A subject who reports more than one treatment AE with the same preferred term will be counted only once for that preferred term using the most extreme incident (i.e., most "severe" for the severity tables and most "related" for the relationship tables).

Adverse events will also be summarized by maximum severity. If a subject has an adverse event with unknown severity, then the subject will be counted in the severity category of "unknown," even if the subject has another occurrence of the same adverse event with a severity present. The only exception is if the subject has another occurrence of the same adverse event with the most extreme severity – "Severe." In this case, the subject will be counted under the "Severe" category.

Adverse events will also be summarized by maximum relationship to study, as assessed by the investigator. If a subject has an adverse event with unknown relationship, then the subject will be counted in the relationship category of "unknown," even if the subject has another occurrence of the same adverse event with a relationship present. The only exception is if the subject has another occurrence of the same adverse event with a relationship assessment of "Reasonable Possibility." In this case, the subject will be counted under the "Reasonable Possibility" category, respectively.

Incidence rates per 100 patient years of exposure to study drug will be presented for AE overviews and for AEs by SOC and preferred term where the number of events will be used as the numerator.

$$100 \times \frac{\text{Number of TEAEs}}{\text{Total Patient Years}}$$

where total patient years is defined as the sum of the study drug exposure of all subjects, as defined in an earlier section, normalized by 365.25, and rounded to 1 decimal place.

Overview of treatment-emergent adverse events and treatment-emergent adverse events during the administration of ABT-494 grouped by System Organ Class and Preferred Term will also be summarized for the Any ABT-494 analysis set by quartile of average daily dose.

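### The extension SAP does not extend its exposure-adjusted AE rates to the individual AESI categories, although the double-blind AE window closes at an efficacy-driven switch

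*SAP*

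**What the plan says.** All references are to the extension SAP unless stated.

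- **AESI table (11.2.2).** "The Adverse Events of Special Interests (AESI) categories will be summarized and presented for each treatment group using SMQ/CMQ/LMQ/Preferred Term". The table below that sentence lists 17 categories with their search definitions. No count, percentage or rate is specified.
- **AE window (11.2.1).** A double-blind event counts if its onset is on or after the first double-blind extension dose and "prior to the open-label dose or up to 30 days after the last dose of double-blind maintenance dose", the latter limb applying to premature discontinuers. Events after a switch are tabulated separately, by open-label dose.
- **Switch (4.2).** Subjects without meaningful symptomatic relief who "meet the criteria for inadequate response at or after Week 20 will be eligible to receive the open-label therapy with ABT-494 12 mg BID". Week 20 is four weeks into "a 36-week double-blind extension phase".
- **Rates (11.2.1).** "Incidence rates per 100 patient years of exposure to study drug will be presented for AE overviews and for AEs by SOC and preferred term". The numerator is the number of events and the denominator is total patient-years.
- **AESI within 11.2.1.** The section announces "An overview of treatment-emergent AEs, including AEs of special interest such as adverse events leading to death", summarised by number and percentage, and its list of AE categories includes "Any treatment-emergent adverse event of special interest".
- **Exposure (9.0).** "Exposure to study drug will be summarized by separately for double-blind extension phase and open-label extension phase". No formula for exposure is given there, although the rate in 11.2.1 refers back to one.

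**The concern.** A switcher can be observed under the randomised dose for about 28 days, a completer for about 252. How often subjects switch may depend on how well the dose works, so observation time can differ systematically between doses. The extension safety set takes in everyone dosed in the extension, including Week 16 non-responders.

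The SAP uses patient-year rates where it judged them useful, but the sentence that does so stops short of the AESI categories. A programmer following the text would probably apply the number-and-percent convention of 11.2.1. Among subjects with equal true risk, the dose that loses more of them to open-label drug would then show fewer AESIs. For this drug class these are the categories a reader will examine for a dose relation: Protocol Section 3.2 names serious infection, malignancy, herpes zoster and hematologic events as open questions for a non-selective JAK inhibitor.

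**Working it through.** The plan states no figure on this point, so there is none to reproduce. The check has two parts.

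**1. Which AESI rows already have a rate?**

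- Any AESI, pooled: yes, because the overview includes AESIs and the overview gets a rate.
- CPK elevation: yes, it is a single preferred term.
- Categories defined by a list of preferred terms (opportunistic infection, herpes zoster, malignancy, neutropenia and similar): no rate is stated. Event rates over a common denominator add, so the category rate can be rebuilt from its preferred-term rates, apart from rounding, by a reader who has the term list.
- Serious infections (the SAE subset of a query) and adjudicated cardiovascular events (committee output): no rate is stated, and preferred-term rates cannot supply one.

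**2. How far could crude percentages mislead?**

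From the documents: first possible switch 4 weeks × 7 = 28 days into the extension; planned length 36 × 7 = 252 days; at most 210 / 3 = 70 subjects per dose, before dropout and ignoring the subjects re-randomised to 24 mg QD before Amendment 2.

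Assumed, because the documents give nothing: the proportion p switching by Day 252; exponential switching from Day 28; the same constant AESI hazard h in both doses; completers observed to Day 252.

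Formulas:

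- λ = −ln(1 − p) / 224
- mean window = 28 + p / λ
- crude risk = 1 − e^(−28h) + e^(−28h) × [h / (h + λ)] × (1 − e^(−224(h + λ))), with h per day

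Example, 60% against 30%. For p = 0.6, λ = 0.9163 / 224 = 0.00409 and the mean window is 28 + 0.6 / 0.00409 = 175 days. For p = 0.3, λ = 0.3567 / 224 = 0.00159 and the mean is 216 days. The ratio is 0.81.

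At a true rate of 10 per 100 patient-years in both doses:

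| Switching, two doses | Mean window (days) | Crude risk | Crude ratio | Difference, subjects of 70 |
|---|---|---|---|---|
| 30% vs 20% | 216 vs 229 | 5.74% vs 6.06% | 0.95 | 0.23 |
| 40% vs 20% | 203 vs 229 | 5.40% vs 6.06% | 0.89 | 0.46 |
| 60% vs 30% | 175 vs 216 | 4.65% vs 5.74% | 0.81 | 0.76 |
| 70% vs 40% | 158 vs 203 | 4.22% vs 5.40% | 0.78 | 0.83 |

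The ratio hardly changes with the hazard; the number of subjects does. At 2 per 100 patient-years the difference is 0.05 to 0.17 subject. At 20 it is 0.43, 0.88, 1.46 and 1.58.

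The timing of switches matters more. If all switchers in both doses switch on one day t, crude risk = (1 − s)(1 − e^(−252h)) + s(1 − e^(−th)), with s the fraction switching. At 10 per 100 patient-years:

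- Day 140, 10% vs 30% switching: 6.38% vs 5.79%, ratio 0.91.
- Day 28, 10% vs 60% switching: 6.08% vs 3.12%, ratio 0.51, or 2.96 points × 70 = 2.1 subjects. This is the extreme of the range examined.

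In every scenario expected events equal h × person-time, so events per patient-year return h in both doses and the rate ratio is 1.0.

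**The case against.** A reader might infer that the AESI table gives only counts and percentages. The text does not say so. Section 11.2.2 names no statistic, and number-and-percent is a default inferred from 11.2.1.

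A reader might also infer that AESIs have no exposure adjustment at all, or that no category rate can be recovered. Neither is right, as the first part of the working shows. Double-blind exposure is also summarised separately with its mean, so mean × N gives approximate patient-years for any reported count.

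Third, a reader might infer that the table will show a false dose-related harm. The documents do not support that. They give no switch rates, and the bias needs unequal or differently timed switching. The switch requires investigator judgement, symptoms and an hs-CRP criterion. Re-randomisation is stratified by induction dose and Week 16 response, so non-responders should be roughly balanced across doses. No between-dose safety tests are planned for the extension.

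Events after the switch are not lost either: they appear by open-label dose, and the Any ABT-494 set runs to study end.

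These points limit the size and reach of the concern. They do not remove it. Tabulating post-switch events elsewhere does not equalise time at risk under the randomised dose, and two clinically important categories still have no planned rate and none that preferred-term rates can supply.

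**Conclusion.** The point holds as a minor gap. The individual AESI categories have no stated statistic and are not covered by the SAP's own exposure-adjusted rates, while the window that feeds them closes at a switch driven by efficacy. If crude percentages are used, any dose with more or earlier switching will look safer than it is.

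With switching spread over the extension, the illustrative crude ratio is 0.78 to 0.95 at equal true rates. That is less than one subject per dose at 10 per 100 patient-years and about 1.5 at 20 with the two largest contrasts. Early clustered and very unequal switching would do more. All of this rests on assumed switch fractions and a constant, equal hazard; the documents fix only the 28-day and 252-day limits and the direction of the effect.

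**What to change.** In Section 11.2.2 of the extension SAP:

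1. State the statistic: n (%) and, beside it, the rate per 100 patient-years for each AESI category by double-blind dose, including serious infections and adjudicated cardiovascular events.
2. State the denominator: time in each subject's double-blind TEAE window, so that it matches the numerator. Say where that window closes for subjects who complete Week 52, since the definition spells out only switchers and premature discontinuers.
3. Use the events-per-patient-year formula of 11.2.1. Subjects with a first event per time at risk, with a confidence interval, is an acceptable alternative but is not required to correct the bias.
4. Say that dose comparisons are read from the rate.

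The cost is a few lines of SAP text and one column per table; the TEAE windows already require the dates. With few events any intervals will be wide, and the rate assumes a roughly constant hazard. It does not remove informative switching, because switchers have poorly controlled disease and may differ in AESI risk.

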11.3 Analysis of Laboratory Data

Changes from Induction Baseline during Extension in continuous laboratory parameters will be summarized by n, mean, standard deviation, and median value value for each treatment group.

Cross (Shift) tables from Induction Baseline to the final value according to the normal range will be provided for each hematology, clinical chemistry parameter and urinalysis parameter except for the microscopic examination.

For selected laboratory parameter with Common Toxicity Criteria (CTC) a listing of all subjects with any laboratory determinations meeting CTC Version 4.03 (or later) of Grade ≥ 3 will be provided. For hemoglobin, an additional list will also be provided based on CTC Version 3.0 (or later) of Grade ≥ 2 . For each of these subjects, the whole course of the parameter will be listed. For subjects with laboratory values with CTC ≥ 3 , all of the laboratory parameters for those subjects will be listed. For subjects with laboratory values with CTC 4, all of the laboratory parameters for those subjects will be listed.

For subjects who switched op open-label therapy, the above tables will also be presented by the open-label dose.

In addition, Cross (Shift) tables from Induction Baseline to the final value according to the normal range will be provided for each hematology, clinical chemistry parameter and urinalysis parameter except for the microscopic examination for the Any ABT-494 analysis set by quartile of average daily dose.

11.3.1 Analysis of Liver Specific Laboratory Tests

According to FDA's Guidance for Industry "Drug-Induced Liver Injury: Premarketing clinical evaluation" (July 2009), when aminotransferase (AT) abnormalities indicating hepatocellular injury are accompanied by evidence of impaired hepatic function (bilirubin elevation $> 2 \times$ ULN), in the absence of evidence of biliary obstruction (i.e., significant

elevation of ALP) or some other explanation of the injury (e.g., viral hepatitis, alcohol hepatitis), the combined finding (i.e., Hy's Law cases) represents a signal of a potential for the drug to cause severe DILI.

For the purpose of assessing for potential Hy's law cases, the frequencies and percentages of subjects with post baseline liver specific function test values that meet the following criteria of potential clinical interest will be summarized by "as treated" treatment group:

- ALT $\geq 3 \times$ ULN
- ALT $\geq 5 \times$ ULN
- ALT $\geq 10 \times$ ULN
- ALT $\geq 20 \times$ ULN
- AST $\geq 3 \times$ ULN
- AST $\geq 5 \times$ ULN
- AST $\geq 10 \times$ ULN
- AST $\geq 20 \times$ ULN
- TBL $\geq 2 \times$ ULN
- Alkaline phosphatase $\geq 1.5 \times$ ULN
- ALT and/or AST $\geq 3 \times$ ULN and concurrent TBL $\geq 1.5 \times$ ULN
- ALT and/or AST $\geq 3 \times$ ULN and concurrent TBL $\geq 2 \times$ ULN

